14.0 SAFETY ANALYSIS

Qualitative tabular record of any AEs.

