8.0 INTERVENTION

Subjects will identify the location of pain on their back. A member of the study team will note the location on a drawing. The TCMS device will be placed at the site the patient

identified. (Low back pain is defined as pain below the costal margin posteriorly, extending as low as the upper buttocks.)

With only a hospital gown intervening, the clinician will place the active or sham TCMS device on the area of pain, turn the device on, and adjust the amplitude upward from 0.24T in increments of 10%, approximately every 6-10 seconds, until the 1.2T setting is achieved or the subject reports discomfort. If the patient reports discomfort, the amplitude will be adjusted downward as necessary to maintain patient comfort.

Treatment group: TCMS device set to 1.2 Tesla will deliver a dose of 10 pulses per minute for 9 minutes (total 90 pulses). The first minute will be dedicated to adjusting the amplitude until maximum is achieved and/or the subject reports a sensation.

Placebo group: the sham TCMS device will remain on the area of pain for 10 minutes. The sham TCMS device is engineered so as to make the same sound at the same intervals as the active device. The same procedures will occur as those with the active device. The first minute will be dedicated to adjusting the “sham” amplitude. The remaining 9 minutes will be the treatment period.

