9.0 ASSESSMENTS

9.1 Numeric Pain Rating Scale (NPRS):

0 to 10 numerical pain rating scale with equally spaced numerical intervals ranging from 0 representing “no pain” to 10 representing the “worst imaginable pain”

9.2 Baseline severity (Pain Diary):

Patient will document in a diary the severity of their pain on each day of the preceding week just prior to treatment.

9.3 Severity during treatment (immediate benefit):

At 5- and 10-minutes

9.4 Severity after treatment is completed (treatment durability):

1, 2, 4, 8, 12, 24, 48 and 72 hours post-treatment.

9.5 We will also follow-up with patients at 7and 30 days post-treatment,

Data collected at baseline, 7 day and 30 day follow-up:

Global Pain Scale (GPS)

Medication usage -Case Report Form

Non-drug treatment -Case Report Form
Functional Status (ADLs, Mobility, Employment)- Case Report Form

Patient satisfaction with treatment- Case Report Form

Presence of unwanted treatment effects, including paresthesia, irritation or discomfort, referred pain, and motor effects. – Case Report Form

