12.0 EFFECTIVENESS OF ANALYSIS

Quantitative, but not statistically powered, trend-analysis of effectiveness of active treatment vs. sham.

Comparison of mean magnitude of treatment effect (change in NPRS) between sham and active treatment (cumulative responder analysis)

Medication usage

Non-drug treatment

Global Pain Scale (GPS)

Patient satisfaction with treatment

Presence of unwanted treatment effects, including paresthesia, irritation or discomfort, referred pain, and motor effects.

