15.0 SAFETY ENDPOINTS

Any undesirable sign or symptom (specific narrative documentation is required for abnormal motor activity, pain of different modality or location, somatic sensations of any kind occurring during treatment)

Serious adverse event (SAE) from any cause precipitating inpatient and/or invasive medical evaluation/treatment

Human factors: detailed evaluation regarding usability, especially

- Misinterpretation of display
- Mistaken entry of intended prescription
- Injury to device operator
- Significant interference with operation of other medical monitoring devices external to the patient

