26.0 DATA ANALYSIS

Descriptive statistics, trend analysis of endpoint means for effectiveness. Tabular collection of adverse events with narrative

STUDY SCHEDULE AND DESCRIPTION OF DATA COLLECTION

Time of data collection	Data collected						
	Log entry	Demographics	History	Informed consent	NPRS first rating or since last rating given	AE	Additional endpoints
*Eligibility screened and offered participation	X	X	X	X			
*Pain each day in 7-day period					X	X	
Day 1 (baseline = start of treatment)					X	X	X
During treatment: 5 minutes					X	X	
10 minutes					X	X	
After treatment: 1 hour					X	X	
2 hours					X	X	
3 hours					X	X	
4 hours					X	X	
8 hours					X	X	
12 hours					X	X	
24 hours					X	X	
48 hours					X	X	
72 hours					X	X	
*Final assessment 7 & 30 days (+3)		X (employment status only)			X	X	X

*Data can be collected in person, via mail, via telephone, email, or fax

LAY SUMMARY

The study will evaluate whether an experimental medical device that emits a brief, intense magnetic field will relieve pain in the low back. The United States Food and Drug Administration (FDA) has approved a similar device for treatment of migraine, but this type of device has not been studied for the treatment of low back pain. No significant adverse reactions or side effects have been reported from the use of magnetic stimulation for headache treatment. Some patients who have migraine headaches have excellent pain relief with the magnetic treatment even if they did not get pain relief with medications.

We do not know whether magnetic treatment will relieve low back pain, so we will test this by applying a powerful electromagnet to the painful area of the low back. In some subjects, the magnet will be turned on, but in other patients the magnet will not be turned on. Neither subjects nor subjects' treating doctor will know whether the magnet was turned on or not, although the study team will know which subjects received treatment with magnetic pulses. The effect on pain will be recorded periodically for 2 days. If the subjects' reported pain is reduced as a result of the magnetic treatment compared with subjects who did not have the magnet turned on, then the magnet might have reduced the pain. Additional studies will be needed to further investigate whether this therapy reduces low back pain.

Keywords: **low back pain, TCMS (Transcutaneous Magnetic Stimulation), TENS (Transcutaneous Electrical Nerve Stimulation)**

RATIONALE AND BACKGROUND

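### The planned safety analysis is a qualitative AE list with no counts by arm and no treatment-emergent rule, so AEs from the session to 72 hours have no stated comparison with sham

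*Combined protocol and SAP*

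**What the plan says.** Safety is part of the stated purpose and objective (Sections 1 and 2), and Section 16 judges 10 subjects per arm enough to show whether the treatment is safe. The analysis behind that judgement is brief:

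- Section 14: "Qualitative tabular record of any AEs".
- Section 26: "Tabular collection of adverse events with narrative".
- Section 15 defines the symptom endpoint as "Any undesirable sign or symptom (specific narrative documentation is required for abnormal motor activity", and the narrative requirement extends to "somatic sensations of any kind occurring during treatment".
- Section 8 has the operator spend the first minute of active treatment "adjusting the amplitude until maximum is achieved and/or the subject reports a sensation".
- The schedule after Section 26 marks AE collection in the row "Pain each day in 7-day period", in the Day 1 row (labelled as baseline and as the start of treatment), and in every later row.
- Section 12 opens with "Quantitative, but not statistically powered, trend-analysis of effectiveness of active treatment vs. sham". Its items include unwanted treatment effects such as paresthesia and motor effects.
- Section 9.5 places the form for those unwanted effects under "Data collected at baseline, 7 day and 30 day follow-up".

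**The concern.** Subjects enter with daily back pain of at least six months, with or without leg pain or nerve compression (Section 18.1). Background symptoms will be common, and some will resemble what a stimulator could cause. The randomized sham arm is the best available guide to how many symptoms would occur without active stimulation, but the safety sections do not say it will be used that way.

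Three decisions are left open:

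- whether an event present before exposure counts;
- whether a neutral sensation during the ramp-up counts as an AE;
- which exposed subjects are in the denominator.

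If these are settled after the data are in, they may be settled by people who know the allocation, because the lay summary says the study team will know who received pulses. Section 13 already expects no AEs. A bare list could then be read as showing safety, or as showing harm, with little support either way.

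**Working it through.** **1. No safety figure to reproduce.** Section 16 gives 20 subjects, 10 per arm, with no event rate, error level or power. The check is therefore a comparison of sections, followed by what 10 per arm can show.

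**2. Which AE data have a stated comparison with sham?** The schedule marks AEs in 14 rows.

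| Period | Rows with AE marked | Stated by-arm analysis |
|---|---|---|
| Before or at start of treatment | 2 (diary week, Day 1) | None for AE entries |
| Session (5 and 10 minutes) | 2 | None |
| 1, 2, 3, 4, 8, 12, 24, 48 and 72 hours | 9 | None |
| Days 7 and 30 | 1 | Unwanted-effects form only, through Section 12 |

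The session and the hours to 72 make 2 + 9 = 11 time points. The schedule agrees with Section 9.5 about the form: its additional-endpoints column is marked only at Day 1 and in the day 7 and 30 row. The uncovered period includes the only exposure, a single session of about 10 minutes, and the three days after it.

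**3. Is there a treatment-emergent rule?** Section 14 covers any AE, Section 15 covers any undesirable sign or symptom, and the schedule collects AEs before exposure. No section says that only events which begin or worsen after the device is switched on are counted. The entries are made by time point, so such a rule could be applied to the planned data.

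**4. Who is in the denominator?** Section 16 counts subjects who complete treatment or sham. Section 17 excludes anyone who cannot tolerate half of the maximum amplitude, which is learned only with the device on. As an assumed illustration, suppose 10 active subjects complete without an event and 2 more stop during the ramp-up because of discomfort. Among completers the rate is 0/10 = 0%; among those exposed it is 2/12 = 16.7%.

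**5. What could counts show at 10 per arm?** The event rates below are assumptions, because the documents give none.

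- Zero events in 10, exact two-sided 95% upper limit: 1 − 0.025^(1/10) = 30.8%. One-sided: 1 − 0.05^(1/10) = 25.9%.
- Chance of at least one event among 10 active subjects: 1 − 0.95^10 = 40% at a true rate of 5%; 1 − 0.90^10 = 65% at 10%.
- Two-sided Fisher exact test: 4/10 versus 0/10 gives p = 0.087; 5/10 versus 0/10 gives p = 0.033.
- Exact power of that test for true rates of 30% versus 10%: 6%.
- Observed 3/10 versus 1/10: difference 20 points, Newcombe 95% interval −16 to +51.

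By-arm counts would thus make the safety data interpretable and show their imprecision. They would not support a formal test, except for very common effects.

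**The case against.** The best defence is that this is a 20-subject preliminary study, for which a descriptive safety table is proportionate, and that by-arm counts can be produced from the data already planned. Both points stand. They limit the fix to description, but they do not supply a rule for what is counted.

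A reader might also infer four stronger things that the documents do not support:

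- *The plan never uses the sham arm for safety.* Section 12 lists unwanted effects within its active-versus-sham analysis. The gap concerns Sections 14, 15 and 26 and the AE entries up to 72 hours. Section 12 names no data source for the item, so linking it to the Section 9.5 form is an inference, though the two items are worded almost identically and the schedule agrees.
- *Pre-treatment complaints are pooled with harms.* No section says so. AEs are recorded by time point and can be separated. Collecting them before exposure is good practice, and the fix depends on it.
- *Active subjects generate AEs by design.* Section 8 lets the ramp end at maximum with no sensation reported, and says that sham subjects go through the same procedures. Section 15 makes the endpoint an undesirable symptom and names sensations under the narrative requirement. A 10/10 active AE rate would be an assumption.
- *Section 14 is why the trial cannot show what the device causes.* Ten per arm limits causal inference however the events are tabulated.

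**Conclusion.** The concern holds as a gap in the stated safety analysis, and the plan should be changed. Sections 14 and 26 give a qualitative list with narrative, no counts by arm and no treatment-emergent rule. AE entries at 11 time points, from 5 minutes to 72 hours, have no stated comparison with sham. This rests on the schedule as printed and on reading the Section 12 item as the Section 9.5 form.

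The effect on the conclusions cannot be given as a number, because the documents state no event rates. What can be said is that even a clean result of 0/10 is compatible with a true rate of up to 30.8%, and Section 16's expectation about safety should be read in that light. The gap does not invalidate data collection: the entries needed for a better table are largely planned already.

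**What to change.** Rewrite Section 14 along these lines:

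- For each event type, report the number and percentage of subjects by arm with exact 95% intervals, labelled descriptive, for the session, to 72 hours and to day 30.
- Count events that begin or worsen after the device is switched on. Use the diary-week and Day 1 entries as each subject's baseline, and state that the Day 1 entry is made before switch-on.
- Use all subjects exposed to active or sham as the denominator, including those who stop early or cannot tolerate the amplitude.
- Show neutral, non-undesirable stimulation sensations on a separate line by arm. Keep all discomfort in the AE counts, including discomfort that led to a lower amplitude; moving it out would hide an effect that Section 12 itself calls unwanted.
- Keep the narratives.
- Reconcile Section 14 with the unwanted-effects item in Section 12: say which data source each uses and how the two tables relate.

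The cost is SAP wording, an onset time on the AE form if it is not already recorded, and slightly more coding work. The intervals will be visibly wide, which is an accurate picture of what 10 per arm can show.

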15.0 SAFETY ENDPOINTS

Any undesirable sign or symptom (specific narrative documentation is required for abnormal motor activity, pain of different modality or location, somatic sensations of any kind occurring during treatment)

Serious adverse event (SAE) from any cause precipitating inpatient and/or invasive medical evaluation/treatment

Human factors: detailed evaluation regarding usability, especially

- Misinterpretation of display
- Mistaken entry of intended prescription
- Injury to device operator
- Significant interference with operation of other medical monitoring devices external to the patient

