11.0 DEFINITION OF SUCCESS

Treatment success is a 30% reduction in mean baseline pain score on the 0 to 10 Numeric Pain Rating Scale (NPRS) that persists at least 1 hour and occurs at any time in the period from treatment through 48-hour follow-up.

Study success is at least 3 of 10 treatment patients meeting the criteria for treatment success and no serious adverse events reported in any subject related to active treatment.

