18.2 EXCLUSIONS

1. Life expectancy ≤ 6 months
2. Oral opiate doses or active ingredient has changed significantly in past 12 months*
3. Received intraspinal medication (e.g., epidural, intrathecal) in the lumbar region of the back within the past 3months
4. Use of intravenous pain medication in the past 3months**
5. Active use of transcutaneous electrical nerve stimulator (TENS) (within 30 days)
6. History of seizures
7. History of implanted medical device, cardiac pacemaker, implantable cardiac defibrillator, or other implant above the knee (Cochlear etc)
8. History of cardiac dysrhythmias
9. Member of a vulnerable population
10. Current or potential legal action of disability claim related to back pain
11. Body Mass Index (BMI) of > 40
12. Another pain condition that might confound results (e.g. back pain above the waistline)
13. Pregnant women
14. Inability to undergo study assessments or complete questionnaires independently
15. Metal objects in the body above knee(i.e. Aneurysm clip, bullet fragment)
16. Active psychological co-morbidities (i.e. uncontrolled schizophrenia)

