23.0 SUBJECT DISCONTINUATION OR STUDY SUSPENSION

Eligible, randomized subjects will be replaced if lost

Study enrollment will be suspended pending principal investigator's decision in response to any SAE

Individual participation will be suspended pending physician disposition in the presence of any SAE

We will request that withdrawn subjects continue to fill out the study questionnaires and allow us to collect data.

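### The only wording that says which SAEs count is tied to inpatient or invasive care, and the success and suspension rules use the term without that limit and without a definition

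*Combined protocol and SAP*

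**What the plan says.** Section 15.0 lists the safety endpoints. One is "Serious adverse event (SAE) from any cause precipitating inpatient and/or invasive medical evaluation/treatment". Another is general capture of adverse events, which begins "Any undesirable sign or symptom (specific narrative documentation is required for abnormal motor activity" and goes on to other kinds of event that need a narrative.

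Section 11.0 makes study success depend on two conditions: at least 3 of 10 active patients meeting the treatment-success criterion, and "no serious adverse events reported in any subject related to active treatment".

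Section 23.0 has two suspension rules: "Study enrollment will be suspended pending principal investigator's decision in response to any SAE" and "Individual participation will be suspended pending physician disposition in the presence of any SAE".

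Section 14.0 gives the whole safety analysis as "Qualitative tabular record of any AEs". Section 26.0 adds narrative to the table. Neither attaches a decision to the tabulated events.

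No section reviewed gives a general definition of seriousness. None names death, a life-threatening event, disability or an otherwise medically important event as making an adverse event serious.

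**The concern.** Someone at the site who has to decide whether an event is an SAE will look for a definition and find only the Section 15.0 line. Its test is whether the event led to inpatient or invasive evaluation or treatment. Taken literally, that leaves out a death at home, a lasting deficit followed as an outpatient, and a seizure assessed and treated non-invasively without admission.

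Such events could well arise away from the site. After the treatment visit, Section 19.0 provides for a telephone call at 48 hours and telephone assessments at 7 and 30 days, so events may be learned of remotely, with no inpatient or invasive care involved.

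What is at stake is the two rules that act on SAEs. Safety is a stated purpose and objective (Sections 1.0 and 2.0), one of the two conditions for study success, and one of the reasons given for the sample size in Section 16.0. If the term that drives the safety condition is narrow or unsettled, the trial could be called a success, or go on enrolling, after an event that most readers would call serious.

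**Working it through.** There is no figure in the plan to reproduce. The sample size in Section 16.0 is set by judgement, with no event rate, so the main check is a comparison of the passages.

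| Section | Use of SAE | Inpatient/invasive limit? | Relatedness condition? | Refers to Section 15.0? |
|---|---|---|---|---|
| 15.0 (endpoint) | SAE that leads to inpatient and/or invasive care | Yes | No, any cause | – |
| 11.0 (study success) | No SAE allowed | No | Yes, related to active treatment | No |
| 23.0 (enrollment and individual suspension) | Any SAE | No | No | No |

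Two readings are open.

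1. *Section 15.0 defines SAE throughout.* A grave event without inpatient or invasive care is then not an SAE. If it is related to active treatment, it need not block success under Section 11.0. Whatever its cause and in either arm, it need not trigger suspension under Section 23.0.
2. *Section 15.0 only selects which SAEs form the endpoint.* The term in Sections 11.0 and 23.0 is then broader and could cover these events, but it has no definition, and both rules rest on an undefined term.

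The documents do not say which reading applies.

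**What one event can do.** One active subject is 1/10 = 10% of the arm. The safety condition tolerates zero related SAEs, so classifying one related event either way settles that condition. It changes the overall declaration only if the 3-of-10 condition is also met.

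**Illustration under assumed rates.** Let p be the true probability that an active subject has a related serious event, and f the share of such events that meet the inpatient/invasive wording. Neither is in the documents; both are assumptions. With independent subjects and n = 10, the probability that at least one counted SAE blocks success is 1 − (1 − p·f)^10.

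| p | f = 1 (all count) | f = 0.75 | f = 0.5 |
|---|---|---|---|
| 5% | 1 − 0.95^10 = 40.1% | 1 − 0.9625^10 = 31.8% | 1 − 0.975^10 = 22.4% |
| 10% | 1 − 0.90^10 = 65.1% | 1 − 0.925^10 = 54.1% | 1 − 0.95^10 = 40.1% |
| 20% | 1 − 0.80^10 = 89.3% | 1 − 0.85^10 = 80.3% | 1 − 0.90^10 = 65.1% |

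At p = 10%, for example, a wording that misses half of the related serious events lowers the chance that the safety condition fails from 65.1% to 40.1%, a drop of 25.0 percentage points. The table shows only how sensitive a zero-event rule is to the definition. It does not estimate the risk of this device.

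**The case against.** The strongest reply is that Section 15.0 is a list of endpoints, not a definitions section. Its line starts from the term SAE and adds a qualifier, so it may simply pick out a subset. Section 23.0 is unqualified, and on the ordinary meaning of the term a death at home would suspend enrollment. This stands. A reader might infer that such events certainly would neither block success nor suspend enrollment; the documents do not support that, because neither Section 11.0 nor Section 23.0 refers to Section 15.0. What remains is that the only wording available permits that result and nothing in the text rules it out.

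Three further points stand in part.

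- *Relatedness.* An unrelated death, or one in the sham arm, would not block success under any definition of SAE, because Section 11.0 counts only events related to active treatment. The gap in the success rule is confined to related events. Section 23.0 has no such condition.
- *Capture.* These events would not go unrecorded. Section 15.0 collects every undesirable sign or symptom, with a narrative for abnormal motor activity, and Section 14.0 tabulates all adverse events. In a single-site trial of 20 subjects the investigator would probably see them. But no rule acts on the table, so the gap lies in the decision rules and not in data collection.
- *Exclusions.* Section 18.2 excludes subjects with "History of seizures" and with cardiac dysrhythmias. A reader might take this as proof that the protocol expects such events. It gives no reason for the exclusions, which may be precautionary, and Section 13.0 says that adverse events are not anticipated. The exclusions make the seizure example a natural one to settle in advance and show no more than that.

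**Conclusion.** The concern holds as a defect of definition. The sole criterion for which SAEs count depends on the care given and literally omits fatal, life-threatening or disabling events without inpatient or invasive care, as well as seizures handled non-invasively as an outpatient. The success and suspension rules use the term with neither that limit nor a definition of their own. Whether a grave event is acted on therefore depends on which reading the site adopts.

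The size cannot be computed from the documents. The effect on study success requires three things together: the event is related to active treatment, it falls outside the inpatient/invasive wording and is classed as non-serious for that reason, and at least 3 of 10 active patients meet the efficacy criterion. The effect on suspension requires only the second. The percentages above rest on assumed rates and carry no weight in this conclusion.

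**What to change.** In Section 15.0, define an SAE by the gravity of the event as well as by the care it leads to. Keep the existing inpatient/invasive wording and add events that are fatal, life-threatening, or cause lasting or significant disability, and other medically important events such as a seizure. The last category is needed because a self-limited outpatient seizure need not meet any of the other three.

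State in Section 11.0 that this definition applies to the success rule, with the relatedness condition left as it is. Section 23.0 must be reconciled with Section 15.0 so that it is clear which events its unqualified term covers.

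The cost is about one sentence in Section 15.0 and a cross-reference in each of Sections 11.0 and 23.0. No new data are needed, since all undesirable signs and symptoms are already collected. The small downside is that slightly more events may qualify as SAEs, which makes the zero-event success criterion somewhat harder to meet.
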